Vitamin D has been shown as an important marker of prognosis in a variety of clinical settings, including overall mortality, acute respiratory distress syndrome (ARDS), infection/sepsis, asthma, cardiovascular disease, diabetes, and pediatric/medical/surgical intensive care unit outcomes. Vitamin D not only plays a role in bone maintenance, but also a variety of extra-axial functions including immune-dysregulation and systemic inflammation. In addition, a number of randomized clinical trials support the supplementation of vitamin D as improving outcome in critical care patients. While the evaluation of vitamin D levels remains a standard-of-care at our institution, the widespread use of vitamin D monitoring and impact on neurocritical care patients remains limited. Our recent prospective observational study of vitamin D levels in neurocritical patients showed that deficiency (<20ng/ml) was highly associated with prolonged hospital stay and increased in-hospital mortality for emergent patients. Moreover, a number of limitations arise from this study due to its observational nature. **This study proposes a randomized, double-blinded, placebo-controlled, single center evaluation of vitamin D supplementation in the neurocritical care patient population (Table 1). Patients admitted to the neurocritical care unit for emergent cases and with vitamin D deficiency (<20ng/ml) will undergo vitamin D serum draw on admission and be randomized to receive cholecalciferol/vitamin D3 supplementation (540,000 IU once orally) or placebo with the primary measured outcome being hospital length-of-stay.** Secondary outcomes will include length of hospital course, length of ICU course, complications, adverse events, discharge Glasgow Outcome Score, in-hospital and 30-day mortality, as well as quality-of-life. Power analysis estimates 198 patients will be needed for each subgroup to determine a 2 day difference in length-of-stay, and we plan to recruit 218 patients per treatment arm to account for dropout, which will take approximately 6-9 months to recruit. Interim analysis and safety monitoring will be performed. We hypothesize that vitamin D supplementation may make a significant impact on reducing morbidity and mortality in the neurocritical care population. The possibility of reducing hospital length of stay and mortality from a simple and cheap intervention such as vitamin D supplementation may be a useful adjuvant treatment in the neurocritical care population.

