4.3. General protocol

1. Patients will be identified through primary treatment teams, including the Departments of Neurosurgery and Neurology, and through screening of the electronic medical record for patients admitted to the NCCU at the University of Utah Health Sciences Center. Patients admitted for non-elective indications as outlined in the inclusion criteria will be enrolled. The full inclusion and exclusion criteria are listed in Table 1. We expect most patients to be admitted to the neurosurgery service and NCCU.
2. A Vitamin D level will be drawn on all non-electively admitted NCCU patients as part of our standard admission protocol.
3. Patients with a Vitamin D level <20ng/ml, defined as deficient, will be consented for the trial. Patients that do not consent for the trial will be studied retrospectively as part of our standard-of-care similarly to our previous prospective trial. Women between 18-45 years of age will undergo a serum or urine pregnancy test to rule out pregnancy prior to enrollment.
4. Patients will be randomized 1:1 to receive Cholecalciferol (Vitamin D3, 540,000 IU once orally or by feeding) immediately or placebo by random number generator. Treatments will be blinded to the patient and physician care teams. Placebos will include similar tablets or liquid formulations that mimic the treatment drug but are indistinguishable.
5. A subsequent Vitamin D level will be drawn 3 days after drug administration or on date of discharge if sooner than 3 days to evaluate the adequacy of vitamin D repletion.
6. Primary outcomes will total hospital length-of-stay. Secondary outcomes will include in-hospital mortality, ICU length-of-stay, ICU complications (rates of sepsis/bacteremia, pneumonia, urinary tract infection), discharge Glasgow Outcome Score, medication adverse events, and quality-of-life metrics. Various patient demographic data will be acquired.
7. Subsequent 30-day mortality will be measured on standard clinical follow-up.

8. 1, 3 month and 6 month Glasgow Outcome Scores and quality-of-life metrics will be obtained. Physical therapy gait distance measurements as well as modified Rankin scale on discharge will be obtained.

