4.9. Power analysis and statistical plan

A variety of variables will be collected on patients (Table 2). We estimated various sample sizes based on our preliminary, prospective, observational trial. Using length-of-stay as a primary outcome, previously we detected a significant decrease in patients with sufficient vitamin D levels ($>20\text{ng/ml}$) (8.21 vs. 6.36 days, $p=0.002$). Using an effect size of 2, alpha of 0.05, 1:1 case/control sampling, we estimate 198 patients will be required per group for this study. We plan to recruit patients to account for a 10% dropout resulting in 218 patients per group, total 436. We also performed power calculations using various other outcomes including, in-hospital mortality, as well as evaluation of both emergent and non-emergent patients. Based on a 6-month timeframe needed to enroll 512 patients in our prospective, observational trial, we estimate the trial would take 12 months for enrollment and randomization in the proposed trial. The primary outcome (length-of-stay) will be measured by T-test as well as multivariate regression to adjust for potential confounders using SPSS (IBM, Armonk, NY). Secondary outcomes will be evaluated by a variety of statistical methods.

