Objectives	
 1. Evaluate the impact of vitamin D supplementation on the length-of-stay of emergent neurocritical care patients (primary outcome) 2. Evaluate the impact of vitamin D supplementation on in-hospital mortality, ICU length-of-stay, Glasgow Outcome Score on discharge, complications, and quality-of-life metrics (secondary outcome)
Primary Aims	Length-of-stay
Secondary Aims	ICU length-of stay, in-hospital mortality, 30-day mortality, ICU complications (sepsis, pneumonia, urinary tract infection), Glasgow Outcome Score, medication adverse events , modified Rankin Scale, physical therapy assessments
Number of Subjects	218 per treatment arm, total 436
Intervention	Vitamin D3 540,000 IU oral vs. placebo
Diagnosis and Main Inclusion Criteria	
Patients >18 years of age
 
Patients admitted to the neurosurgery or neurology services
 
Patients admitted to a critical care unit
 
Informed consent
 
Expected to stay in the ICU for 48 hours or more
 
Vitamin D deficiency (<20ng/ml)

Exclusion criteria	
Patients where a vitamin D level was not drawn within 48 hours of admission
 
Patients not randomized within 48 hours of admission
 
Readmitted patients to the critical care unit
 
Lack of informed consent
 
Prior supplementation with vitamin D
 
Severely impaired gastrointestinal function
 
Other trial participation
 
Pregnant or lactating women
 
Hypercalcemia (total calcium of >10.6 mg/dL or ionized serum calcium of >5.4 mg/dL)
 
Tuberculosis history on clinical exam
 
Sarcoidosis history on clinical exam
 
Nephrolithiasis within the prior year
 
Patients not deemed suitable for study participation (ie, psychiatric disease, living remotely from the clinic, or prisoner status)
 
Pregnant or nursing women

Data and safety	Monthly review of data entry

monitoring	Quarterly independent review of data safety metrics Daily review of patient neurological exam, and laboratory values (CBC, BMP, calcium, phosphate) Interim 6-month data analysis
Statistical Methodology	T-test (parametric), Chi-square (non-parametric), univariate regression, multivariate linear regression, logistic regression, Kaplan-Meier survival, Cox proportional hazards modeling, interim analysis SPSS (IBM, Armonk, NY)

Table 2: Demographic, Clinical, and Safety Variables

Demographic Variables

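### On the usual reading of 10% dropout, 218 per group leaves about 196 evaluable patients, not the 198 that section 4.9 requires

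*Combined protocol and SAP*

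**What the plan says.** Section 4.9 of the combined protocol and SAP gives the requirement: "we estimate 198 patients will be required per group for this study". The next sentence adds the allowance: "10% dropout resulting in 218 patients per group, total 436". The inputs named for the 198 are "Using an effect size of 2, alpha of 0.05, 1:1 case/control sampling"; neither the target power nor the standard deviation is given.

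The opening summary repeats both numbers. It says that "198 patients will be needed for each subgroup to determine a 2 day difference in length-of-stay" and then "we plan to recruit 218 patients per treatment arm to account for dropout". Table 1, under number of subjects, gives only the recruitment figure: "218 per treatment arm, total 436". Allocation is 1:1 (section 4.3).

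The documents do not print the inflation formula and do not say what the 10% is a percentage of. They describe no other allowance. Table 1 lists an interim analysis, but no sample-size adjustment is attached to it.

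**The concern.** A dropout allowance is meant to leave the required number once the stated fraction has been lost. Losses come out of the patients recruited, so the recruitment target is the requirement divided by one minus the dropout fraction. Multiplying the requirement by one plus the fraction always gives a slightly smaller number, and 218 is what that multiplication yields here.

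What is at stake is whether the text is consistent with itself. The recruitment target is a headline figure, and a reader who takes 10% off 218 arrives at 196 and cannot reconcile it with the 198 given one sentence earlier. Almost nothing is at stake in the performance of the trial, as the working shows.

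**Working it through.** **Inputs.** From section 4.9: 198 required per group, 10% dropout, 218 recruited per group (436 in total), difference of 2 (days, according to the opening summary), alpha 0.05. Not in the documents, so assumed: power (80% and 90% both tried), two-sided testing, and an SD solved from n = 198.

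**1. Reproduce the plan's figure.** Requirement x (1 + dropout) = 198 x 1.1 = 217.8, rounded up to 218; 2 x 218 = 436. Both stated figures are matched.

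**2. Apply the stated dropout to the stated recruitment.** 218 x (1 - 0.10) = 196.2 evaluable per group. The shortfall is 198 - 196.2 = 1.8, about 2 per group.

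**3. Dropout that 218 does cover.** 1 - 198/218 = 0.0917, or 9.2%.

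**4. Recruitment that would leave 198.** 198/(1 - 0.10) = 220 per group, 440 in total. Check: 220 x 0.9 = 198. This is 2 more per group and 4 more overall than stated.

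**5. Cost in power, under assumptions.** With the normal approximation for two means, power = Φ(δ / (SD x √(2/n)) - 1.960). The SD is the value at which n = 198 gives the assumed power: SD = δ / ((1.960 + z) x √(2/198)), with δ = 2 days and z the normal quantile for that power.

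| Assumed power at 198 | z | Implied SD (days) | Power at 196 | Loss (points) |
|---|---|---|---|---|
| 80% | 0.842 | 7.10 | 79.6% | 0.4 |
| 90% | 1.282 | 6.14 | 89.7% | 0.3 |

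One-sided testing at 0.05 changes the implied SDs (8.00 and 6.80 days) but gives the same loss to within 0.1 point.

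**The case against.** **The base of the 10% is not stated.** If the allowance means 10% of the required 198 added on top, 218 is exact and nothing is wrong. This stands as far as it goes: both the multiplication and the base are inferred, the first from the exact numerical match. But the sentence in section 4.9 is about how many patients to recruit, and the withdrawals described in section 4.4 are of enrolled participants. Nothing in the documents defines dropout as a share of completers. Even on the kinder reading, the sentence needs a clarifying clause.

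**A shortfall is not certain.** Any dropout up to 9.2% still leaves 198, and 10% is a round figure offered without support. This is true, but the plan chose 10% and says that 218 accounts for it.

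**Dropout may not remove the primary outcome.** Length of stay comes from chart dates, and Table 2 collects admission and discharge dates. A withdrawn patient's stay might still be known, in which case the loss would be smaller or nil. The plan does not say whether such data are kept, so this mitigation is possible but cannot be relied on.

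**The 198 is itself soft.** Section 4.9 rounds an observed difference of 8.21 - 6.36 = 1.85 days to 2. With all else fixed, using 1.85 would give about 198 x (2/1.85)² = 231 per group. Together with the unstated SD and power, that is a larger uncertainty than two patients. It is a fair reason to rank this point low, but it does not make the dropout arithmetic right.

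**Stronger readings.** A reader might infer that the trial is underpowered, or that enrolment must rise to 220 per group. The documents support neither: they state no target power, and on the assumptions above the loss is under half a percentage point. A reader might also infer that the three places conflict. They do not; all give 218, and Table 1 mentions neither 198 nor dropout.

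**Conclusion.** Wrong as written, and minor. On the usual reading, 218 per group with 10% dropout leaves about 196 evaluable patients, about 2 per group below the plan's own 198. The size of the shortfall rests on two assumptions: that the 10% applies to those recruited, and that a patient who drops out contributes no length-of-stay value. The power cost of 0.3 to 0.4 points further assumes that 198 was set for 90% or 80% power. The point changes no decision about design or analysis and says nothing on whether 198 is the right requirement, which cannot be checked without the SD and power.

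**What to change.** In section 4.9, restate the sentence so that it is true of its own numbers: 218 per group (436 in total), giving about 196 evaluable per group after 10% of recruited patients are lost. Equivalently, say that 218 per group retains 198 evaluable with dropout of up to 9.2%. Either wording also settles the base of the percentage.

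Carry the same evaluable number into the opening summary, which also cites 198 and 218. Table 1 can stay at 218 per arm, 436 in total.

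The cost is one reworded sentence in two places, with no extra enrolment. Moving to 220 per group (440 in total) would restore 198 exactly, but a shortfall of this size does not call for it.

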2. Background/Rationale

Hypovitaminosis D has a high prevalence among the general population, with some studies showing over half of the elderly population being affected (Chapuy 1997). Among critically ill patients, various studies have shown associations between hypovitaminosis D and multiple negative outcomes including mortality (De Haan 2014,

Rech 2014), ARDS (Dancer 2015), and infection (Flynn 2012). Vitamin D deficiency has also been shown to have impacts on various neurological diseases such as stroke (Yalbuздag 2015, Chung 2015), and dementia (Littlejohns 2014). While the mechanism between vitamin D deficiency and these diseases is not entirely known, evidence suggest that vitamin D can affect vascular reactivity, inflammation, and the immune system (Carthy 1989, Vargas-Vasserot 2011) (Table S1, Figure S1-2).

Vitamin D has been shown to impact prognosis in a variety of retrospective and randomized clinical trials within an intensive care unit (ICU) environment (Amrein 2011). **Despite these findings, there have been no studies examining the impact of hypovitaminosis D in specialized neurocritical care units (NCCU).** Given the often significant differences in the management of patients in NCCU and more generalized intensive care units (Kurtz 2011) there is a need for further inquiries into the impact of low vitamin D levels in this specific environment. **This study proposes a randomized, double-blinded, placebo-controlled, single center evaluation of vitamin D supplementation in the emergent NCCU patient population (Table 1).** We have previously conducted a prospective, observational analysis of 823 NCCU patients and shown a significant reduction in hospital length-of-stay for all patients (7.14 vs. 5.97 days, $p=0.0018$) and for emergent cases (8.21 vs. 6.36 days, $p=0.038$), as well as reduced in-hospital mortality for emergent patients with non-deficient vitamin D levels (26/203 vs. 22/321, $p=0.021$). Nevertheless, these results remain limited in being observational studies without randomization or controls.

3. Study purposes and objectives

1. Evaluate the impact of vitamin D supplementation on the length-of-stay of emergent neurocritical care patients (primary outcome)
2. Evaluate the impact of vitamin D supplementation on in-hospital mortality, ICU length-of-stay, Glasgow Outcome Score on discharge, complications, and quality-of-life metrics (secondary outcome)

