3. Evaluate the impact of vitamin D supplementation on Glasgow Outcome score and quality-of-life metrics at 3 and 6 months post-discharge (secondary outcome)

4. Methods

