4.10. Funding source

Planned sources of funding for this study are from internal departmental grants without potential for conflicts-of-interest. No submission for additional funding sources is planned at this time.

5. Anticipated results and potential public health impact

The potential benefit of this study would include knowledge about the success of vitamin D supplementation on various critical care outcomes. While they may not directly apply to a patient, they can be useful to additional critical care patients admitted an ICU in the future. The societal benefit will include reduced patient morbidity and mortality, as well as shorter hospital stays and therefore reduced ICU expenditure. Vitamin D is a relatively cost-effective medication that is well-tolerated. Its potential impact to reduce hospital stays, by even 1 day would play a significant role in reducing patient cost, disease morbidity, and risk from hospitalization. Future research directions can involve a multi-center randomized clinical trial to validate the effect of vitamin D in the neurocritical care patient as well as further molecular studies evaluating the non-skeletal effects of vitamin D. Additional, studies on vitamin D as a biomarker and effects on a cellular level can also be forthcoming if a potential benefit is identified clinically. Identification of the molecular mechanisms by which vitamin D may alter disease pathology may serve as a method for the development of additional treatments.

6. Protocol amendments

6.1. 1/10/17, Addition of phone consents as well as two study co-investigators, [name] and [name] was performed. Repeat vitamin D levels at 3 days following administration of study drug or placebo was modified from prior planned repeat vitamin D at 7 days.

6.2. 8/6/17, Addition of physical therapy assessment and modified Rankin scale as secondary outcomes of the study. Change of study faculty sponsor from [name] to [name] as [name] is leaving the University of Utah.

Table 1: Summary of Study Characteristics	
Title	Randomized Clinical Trial of Hypovitaminosis D Treatment in the Neurocritical Care Unit
Methodology	Randomized, double-blinded, placebo-controlled clinical trial
Study Duration	1-1.5 years (12 months recruitment, 3-6 month analysis)
Study Center(s)	University of Utah Health Sciences Center

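### Do the two recruitment periods (6 to 9 and 12 months) and a study duration without a follow-up term call for a change to the plan?

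*Combined protocol and SAP*

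**What the plan says.** - **Opening summary:** 218 patients per arm, "which will take approximately 6-9 months to recruit".
- **Section 4.9:** "Based on a 6-month timeframe needed to enroll 512 patients in our prospective, observational trial, we estimate the trial would take 12 months". The basis is the sponsor's earlier observational cohort. The section does not say who the 512 were, what share was vitamin D deficient, or what share would be eligible and consent.
- **Table 1, Number of Subjects:** "218 per treatment arm, total 436".
- **Table 1, Study Duration:** "1-1.5 years (12 months recruitment, 3-6 month analysis", with no separate follow-up term.
- **Table 1, Data and safety monitoring:** "Interim 6-month data analysis", with no patient number attached.
- **Section 3, objective 3:** Glasgow Outcome Score and "quality-of-life metrics at 3 and 6 months post-discharge". Section 4.3 item 8 and Table 2 also call for 6-month outcomes. The objectives listed in Table 1 stop at objective 2.
- **Section 2:** the earlier work was an "observational analysis of 823 NCCU patients". Its in-hospital mortality figures for emergent patients use denominators of 203 deficient and 321 non-deficient.

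All of this is current text. The amendment entries in section 6 do not mention the timeline.

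**The concern.** Two points look wrong on a first reading.

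First, one recruitment target has two durations, and the longer is up to twice the shorter. Only deficient patients can be randomised, so a forecast built on all patients in an earlier cohort may be optimistic. If accrual fell well short, the trial might close below 436 and lose power.

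Second, the stated duration appears to leave no room for the 6-month outcomes. If 3 to 6 months is analysis time, follow-up is missing. If it is follow-up, 12 + 6 = 18 months uses the whole allowance and leaves nothing for analysis. Objective 3 would be at risk for patients enrolled late. A look at 6 months would also cover a very different share of the trial depending on which recruitment period applies.

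**Working it through.** **Inputs.** 512 patients in 6 months, 198 per group and 10% dropout (section 4.9); 436 in total (Table 1); 203 deficient and 321 non-deficient emergent patients, 823 patients overall, and a mean stay of 8.21 days in deficient emergent patients (section 2); 6-month follow-up (objective 3); 3 to 6 months of analysis (Table 1).

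**1. The plan's own figures.** Sample size: 198 × 1.10 = 217.8, rounded to 218, and 2 × 218 = 436. Time does not enter this.

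Recruitment: 512/6 = 85.3 per month. If every patient qualified, 436/85.3 = 5.1 months. Twelve months needs 436/12 = 36.3 per month, which is 36.3/85.3 = 42.6% of the earlier rate. The plan states no such yield, so the 12 months cannot be strictly reproduced, but it clearly allows for most patients not being randomised.

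**2. Do the plan's data contradict 12 months?** Assume the 512 were emergent patients and all deficient patients are recruited. Deficient share: 203/(203 + 321) = 38.7%. Accrual: 85.3 × 0.387 = 33.1 per month. Relative standard error, treating the 512 as Poisson and independent of the share: √(1/512 + (1 − 0.3874)/203) = 0.0705. The range is the expected count × (1 ± 1.96 × 0.0705).

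| Recruitment | Rate needed for 436 | Expected | Range |
|---|---|---|---|
| 6 months | 72.7/month | 198 | 171–226 |
| 9 months | 48.4/month | 298 | 256–339 |
| 12 months | 36.3/month | 397 | 342–452 |

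Assume instead that the 512 had the mix of all 823. The other 823 − 524 = 299 have an unknown deficient share, between none and all. The overall share then lies between 203/823 = 24.7% and 502/823 = 61.0%. That gives 189–468 patients at 9 months and 253–625 at 12, and both ranges contain 436.

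These counts precede exclusions and refusals, and they omit patients from other ICUs, whom section 4.7 admits. They make 6 months look short on either assumption. They do not show 12 months to be wrong.

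**3. Duration.** Table 1's own parts give 12 + 3 = 15 to 12 + 6 = 18 months, so its 1-year lower end fails on its own terms. Adding 6 months of follow-up before analysis:

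| Recruitment | Last 6-month visit (plus hospital stay) | With 3–6 months' analysis |
|---|---|---|
| 6 months | month 12 | 15–18 months |
| 9 months | month 15 | 18–21 months |
| 12 months | month 18 | 21–24 months |

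The stated 1.5 years therefore holds with 6 months of recruitment, holds with 9 only if analysis takes 3 months, and fails with 12.

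**4. What uses these figures?**
- *Sample size:* set by the effect, alpha and dropout. No duration is used.
- *Primary comparison:* hospital stay is complete at discharge. Neither the t-test nor the regression uses calendar time.
- *Six-month outcomes:* fixed per patient and counted from discharge. No text cancels them at a study end date.
- *Six-month look:* set by calendar. If counted from first enrolment with even accrual, it falls at 6/6 = 100%, 6/9 = 67% (291) or 6/12 = 50% (218) of enrolment. The plan attaches no stopping boundary or information fraction to it, so none of its rules depends on which share applies.

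**The case for a change.** The best case for a change is that Study Duration might be enforced as a closing date, especially as section 4.10 relies on internal departmental funds with no further application planned. With 12 months of even recruitment (36.3 per month), closing at month 15 would cut off the 6-month outcome for those enrolled after month 9: 3 × 36.3 = 109 of 436, or 25%. Closing at month 18 would cost only patients whose stay carries the visit past that date: 8.21/30.4 × 36.3 ≈ 10, or 2%. It can also be said that a look taken after 6 months of a 6-month recruitment is hardly interim, and that the correction costs only a few words.

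Part of this stands. The two recruitment periods do conflict, Table 1's sum is wrong, and a budget built on 1.5 years would be short if recruitment takes 12 months. The step from there to lost data does not stand. Table 1 describes an expected duration, section 4.9 presents its figure as an estimate, and the summary's figure is approximate. Nothing says that follow-up stops on a date, whereas objective 3, section 4.3 item 8 and Table 2 all require the 6-month assessments. Staff following the plan would keep collecting them. Giving the interim look as a patient count would add detail without altering any rule in the plan.

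**Conclusion.** The inconsistency is genuine but clerical. Recruitment is forecast as 6 to 9 months in one place and 12 in two others. Table 1's range should span 15 to 18 months on its own parts, and it leaves unclear whether follow-up is included. A realistic total is 21 to 24 months with 12 months of recruitment, or 15 to 21 with 6 to 9, if analysis follows the last 6-month assessment.

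No estimate, test, sample size or assessment schedule changes with the figure used. Followed as written, the trial still enrols 436 patients and still collects 6-month outcomes. The accrual arithmetic makes the shorter forecast doubtful if the 512 were emergent patients, but it rests on an unstated case mix and on full eligibility and consent, so it cannot show the 12-month estimate to be wrong.

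This conclusion assumes that the stated duration is a forecast rather than a closing date. The documents support that reading and contain nothing against it. No change to the plan follows.
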